8.2 Randomization

The study is a randomized, active-controlled, and open-label study. Eligible subjects will be randomly assigned into either the avelumab arm or control group in a 1:1 ratio after 12-week chemotherapy in the Induction Phase. The randomization will be stratified by region (Asia versus non-Asia). The purpose of the stratification is to ensure a balance of the treatment arms within each region. Randomization will occur using the IWRS as described in Section 2 upon completion of the Induction Phase and determination of subject eligibility.

8.3 Endpoints

8.3.1 Primary Endpoint

The primary endpoint of the trial is OS, defined as the time (in months) from randomization to the date of death, regardless of the actual cause of the subject's death.

The survival follow-up will continue until 5 years after the last subject receives the last dose of avelumab. For subjects who are still alive at the time of data analysis or who are lost to follow-up, OS will be censored at the last recorded date that the subject is known to be alive (date of last contact, last visit date, date of last randomized treatment administration, or date of last scan, whichever is the latest) as of the data cut-off date for the analysis.

8.3.2 Secondary Endpoints

The secondary endpoints, which correspond to the Maintenance Phase in this trial, are the following:

- PFS in all randomized subjects according to RECIST v1.1, per Investigator assessment
- BOR in all randomized subjects according to RECIST v1.1, per Investigator assessment
- Subject-reported outcomes / QoL
- Safety and tolerability in all subjects.

8.3.2.1 Progression-Free Survival

Progression-Free Survival, defined as the time (in months) from randomization to the date of the first documentation of objective PD or death due to any cause (whichever occurs first), is the first key secondary endpoint of the study. The date of the first documented objective PD will be determined according to RECIST v1.1 based on Investigator response assessment.

The PFS data will be censored on the date of the last adequate tumor assessment for subjects who do not have an event (PD or death), for subjects who start new anticancer treatment prior to an event, or for subjects with an event after 2 or more missing tumor assessments. Subjects who do not have a baseline tumor assessment or who do not have any post-baseline tumor assessments will be censored on the date of randomization unless death occurred on or before the time of the second planned tumor assessment, in which case the death will be considered an event.

8.3.2.2 Best Overall Response

Best Overall Response in Maintenance Phase is the key secondary endpoint for the study. The confirmed BOR will be determined according to RECIST v1.1, per Investigator assessment, and statistically evaluated as the ORR. BOR is defined as the best response obtained among all tumor assessment visits after the date of randomization until documented disease progression.

For a BOR of PR or CR, confirmation of the response according to RECIST v1.1 will be required, preferably at the regularly scheduled 6-week assessment interval but no sooner than 4 weeks after the initial documentation of CR or PR. Confirmation of PR can be confirmed at an assessment later than the next assessment after the initial documentation of PR. A BOR of SD requires that an overall response of SD has been determined at a time point at least 6 weeks after randomization.

The ORR is defined as the proportion of all randomized subjects with a confirmed BOR of PR or CR according to RECIST v1.1, as per Investigator assessment.

8.3.2.3 Subject-Reported Outcomes / Quality of Life

The following subject-reported outcomes are further secondary endpoints for maintenance therapy:

- EQ-5D-5L
- EORTC QLQ-C30
- EORTC Gastric Cancer Module QLQ-STO22.

8.3.3 Safety Endpoints

Safety endpoints include AEs, physical examinations, clinical laboratory assessments, concomitant medications, vital signs, ECG parameters, and ECOG PS.

8.4 Analysis Sets

Screening Analysis Set

The Screening Analysis Set includes all subjects who signed the ICF.

Intention-to-Treat (ITT) Analysis Set

The ITT Analysis Set will include all subjects who were randomly assigned to Maintenance Phase study treatment. Analyses performed on the ITT Analysis Set will be performed according to subjects' treatment arms, as randomized. The ITT Analysis Set will be the primary analysis set for all primary and secondary efficacy endpoints.

Per-Protocol Analysis Set

The Per-Protocol (PP) Analysis Set will include all ITT subjects who did not have clinically important protocol deviations. Clinically important protocol deviations will be specified in the trial SAP.

PD-L1+ Analysis Set

The PD-L1+ Analysis Set is a subset of the ITT Analysis Set consisting of all PD-L1+ subjects determined by the PD-L1 IHC 73-10 pharmDx companion diagnostic assay. Analyses performed on the PD-L1+ Analysis Set will be performed according to subjects' treatment arms as randomized. One of two primary hypotheses for OS subjects will be tested in the PD-L1+ Analysis Set.

Health-Related Quality of Life Analysis Set

The HRQoL Analysis Set is a subset of the ITT Analysis Set and includes all ITT subjects who meet both of the following criteria:

- Re-baseline HRQoL assessment completed
- At least one Maintenance Phase HRQoL assessment completed.

Re-baseline HRQoL assessment occurs following completion of Induction Phase chemotherapy treatment at the Re-baseline visit, which should occur within the 10-day Re-baseline period.

Maintenance Phase HRQoL assessment is defined as HRQoL questionnaires completed after the first dose of Maintenance Phase study treatment for subjects who received avelumab or continuation of Induction Phase chemotherapy treatment, and HRQoL questionnaires completed after date of randomization for subjects on BSC-only.

Safety for Induction Phase (Safety-Induction) Analysis Set

The Safety-Induction Analysis Set will include all subjects who were enrolled into the study (ie, signed informed consent) and received at least 1 dose of Induction Phase chemotherapy. Analysis for the Safety-Induction Analysis Set will be summarized for all subjects as one single group.

Safety for Maintenance Phase (Safety-Maintenance) Analysis Set

The Safety-Maintenance Analysis Set will include all subjects who received at least 1 dose of randomized treatment or who were assigned to receive BSC-only in the Maintenance Phase. Analyses performed on the Safety-Maintenance Analysis Set will consider subjects as treated.

8.5 Description of Statistical Analyses

8.5.1 General Considerations

Full details of all planned analyses will be described in the trial SAP. The SAP may modify the plans outlined in the protocol; however, any major modifications of planned analyses will be reflected in a protocol amendment if it is modified before data unblinding. If, after the trial is unblinded, changes are made to the SAP, then these deviations to the plan will be documented in the Clinical Trial Report.

All safety and efficacy endpoints will be summarized by treatment arm with the exception of endpoints corresponding to the Induction Phase which will be summarized by total number of subjects.

In order to provide overall estimates of treatment effects, data will be pooled across trial centers. The “center” factor will not be considered in statistical models or for subgroup analyses due to the high number of participating centers in contrast to the anticipated small number of subjects randomized at each center.

In general, continuous variables will be summarized using number (n), mean, median, standard deviation, minimum, and maximum. Categorical variables will be summarized using frequency counts and percentages.

The calculation of proportions will be based on the number of subjects in the Analysis Set of interest, unless otherwise specified in the trial SAP.

Baseline

For the Induction Phase, baseline is defined as the last measurement taken prior to the first dose of treatment during the Induction Phase. For the Maintenance Phase, baseline is defined as the last measurement taken prior to the first dose of randomized treatment for safety endpoints and the last measurement taken prior to randomization for efficacy endpoints. If such a value is missing, the last measurement prior to the first dose of randomized treatment will be used as the baseline measurement for the efficacy analysis except for analyses of tumor assessments data where the Baseline assessment would be considered missing. For subjects who received BSC-only, baseline is defined as the last measurement taken prior to randomization for both safety and efficacy

endpoints. Baseline for heart rate and QTc assessments will be derived from the visit where both heart rate and QT are not missing.

On-Treatment

For the Induction Phase, the on-treatment period is defined as the time from the first administration of chemotherapy to the last administration of chemotherapy + 30 days, the earliest date of subsequent anticancer drug therapy - 1 day, or the date of randomization into the Maintenance Phase - 1 day, whichever occurs first.

For subjects randomized to active Maintenance Phase study medication, the on-treatment period is defined as the time from the first study treatment administration to the last study treatment administration date + 30 days or the earliest date of subsequent anticancer drug therapy minus 1 day, whichever occurs first, unless otherwise stated. For subjects who received BSC-only, study treatment is considered to start on the day of randomization and end on the earliest date from among the following: the date given on the End of Assessment and Study Termination eCRF pages, date of death.

Multiple Comparison Strategy

A hierarchical test strategy will be used to control the overall type I error rate for the primary endpoint OS and key secondary endpoints of PFS and BOR in the following hierarchical order:

- 1: OS in the ITT Analysis Set and the PD-L1+ Analysis Set in the Maintenance Phase
- 2: PFS in the ITT Analysis Set in the Maintenance Phase
- 3: BOR in the ITT Analysis Set in the Maintenance Phase

The overall 2.5% (1-sided) type I error will be split between OS in all randomized subjects and PD-L1+ subjects with 2.0% (1-sided) and 0.5% (1-sided), respectively. One interim analysis is planned for OS in all randomized subjects. OS in PD-L1+ subjects will be tested at the primary analysis only. A Lan-DeMets alpha spending function for O'Brien-Fleming boundaries will be used to control the overall type I error rate of OS in all randomized subjects at 2% between the interim and primary analysis (see Section 8.6).

For the primary endpoint, a closed testing procedure with weighted Bonferroni tests, described by [Hommel 2007](#) will be used for determining significance of the dual hypothesis primary testing. The summary is briefly described as follows (detailed process is in the study SAP).

If any of the two null hypotheses of OS (evaluated in all randomized subjects and in PD-L1+ subjects) is rejected, the corresponding alpha level will be recycled between both populations. The alpha recycling approach is as follows:

1. If the null hypothesis of OS in all randomized subjects is rejected at either the interim or the primary analysis, the 2% (1-sided) alpha allocated to OS in all randomized subjects

will be recycled to OS in PD-L1+ subjects, then 2.5% (1-sided) alpha level will be used for OS in PD-L1+ subjects.

2. If the null hypothesis of OS in PD-L1+ subjects at the primary analysis is rejected, the 0.5% alpha allocated to OS in PD-L1+ subjects will be recycled to OS in all randomized subjects. In this case, the significance will be based on a local 2.5% (1-sided) alpha level for OS in all randomized subjects. Assuming the planned number of events are observed at each analysis, the 1-sided boundaries would then be 0.0233 for OS in all randomized subjects at primary analysis. This has been recalculated by keeping the alpha level of 0.0072 at interim analysis unchanged.

PFS, followed by BOR, will be tested if and only if both null hypotheses for OS in all randomized subjects and PD-L1+ subjects are rejected. In that case, PFS will be tested with full 2.5% (1-sided) type I error at the primary analysis. BOR will be tested with full 2.5% (1-sided) type I error at the primary analysis after the null hypothesis of PFS is rejected. All analyses including OS in PD-L1+ subjects, PFS and BOR will be exploratory if the study is stopped at interim based on rejection of null hypothesis of OS in all randomized subjects.

No formal adjustment for multiplicity will be undertaken for non-key secondary endpoints, sensitivity analyses, or exploratory analyses.

Statistical analyses will be performed using SAS® version 9.4 or higher.

8.5.2 Analysis of Primary Endpoint

Primary Analysis

The primary endpoint for maintenance therapy is OS. The two primary analysis sets will be the ITT Analysis Set and the PD-L1+ Analysis Set. The following analysis will be conducted in the same manner for both ITT and PD-L1+ Analysis sets. The difference between the two treatment arms will be compared using a stratified, 1-sided, log-rank test. The stratification factor will be region (Asia versus non-Asia). Control of type I error and statistical significance is discussed in Section 8.5.1. The following null hypothesis will be tested:

$$H_0: \lambda_A(t) / \lambda_B(t) \geq 1, \text{ versus } H_1: \lambda_A(t) / \lambda_B(t) < 1$$

where $\lambda(t)$ represents the hazard rate (corresponding to each endpoint) at time t for treatment arms A (avelumab) and B (continuation of the same chemotherapy regimen/BSC).

A stratified Cox proportional hazards model will be used to assess treatment effect between the two treatment arms and to explore the robustness of the primary endpoint confirmatory analysis. The natural parameter of this model is the log hazard ratio. Each stratum will define a separate baseline hazard function. Ties will be handled by replacing the proportional hazards model by the discrete logistic model. The hazard ratio of avelumab versus maintenance chemotherapy/BSC (with maintenance chemotherapy/BSC as reference) together with the corresponding Wald 2-sided 95% CIs will be presented.

Kaplan-Meier (ie, product-limit) estimates of median OS will be presented by treatment arm together with 2-sided 95% CIs calculated according to [Brookmeyer and Crowley \(1982\)](#). Finally, the number of subjects at risk vs. failed along with Kaplan-Meier estimates of survival probability (often referred to as “survival rate”) at 3, 6, 9 and 12 months will be estimated with corresponding 2-sided 95% CIs derived using the log-log transformation according to [Kalbfleisch and Prentice \(1980\)](#).

The number and percentage of subjects with observed OS events will be presented by treatment arm (avelumab or maintenance chemotherapy/BSC). In addition, frequency counts for censoring reason will be presented by treatment group.

Sensitivity Analyses

The following sensitivity analyses for OS will be performed to explore the robustness of the primary confirmatory analyses. These sensitivity analyses will be performed in the same manner for both ITT and PD-L1+ analysis sets. Additional sensitivity analyses may be specified in the trial SAP.

- The primary endpoint analysis will be repeated based on the PP Analysis Set if this analysis set includes less than 90% of subjects in the ITT Analysis Set.
- An unstratified analysis will be performed comparing OS between the treatment arms.
- If the actual number of events is 10% more than the planned number at the primary analysis, the primary analysis of OS will be repeated by using the date at which exactly 356 events in all randomized subjects were observed, or after a minimum follow-up of at least 18 months after randomization, whichever occurs last.

The following analyses will also be performed:

- The validity of the proportional hazards assumption will be assessed visually by plotting $\log(-\log(\text{survival}))$ versus $\log(\text{time})$ by treatment arm.
- A Kaplan-Meier plot for OS follow-up duration will also be generated to assess the follow-up time in the treatment arms by reversing the OS censoring and event indicators.

8.5.3 Analysis of Secondary Endpoints

Based on the hierarchical testing strategy described in Section 8.5.1, PFS and BOR will be tested at the primary analysis, if, and only if, both of hypotheses testing OS (in all randomized subjects and PD-L1+ subjects) reach statistical significance.

8.5.3.1 Key Secondary Endpoint – Progression-Free Survival

The statistical analysis of PFS per Investigator assessment will be the same as described for the primary analysis of OS.

In addition, the following sensitivity analyses of PFS will be performed:

- Events (PDs/deaths) after the start of new anticancer treatment will be considered as events
- Clinical progression will be considered as an event
- Counting all PD and deaths as events regardless of missing assessments or timing of the event.

8.5.3.2 Key Secondary Endpoint – Best Overall Response

For the analysis of BOR in the Maintenance Phase (see Section 8.5.3) according to RECIST v1.1 and per Investigator assessment, the ORR (defined as having a confirmed BOR of CR or PR) will be calculated along with corresponding 2-sided exact Clopper-Pearson 95% CIs for the two treatment arms. The Cochran-Mantel-Haenszel test will be stratified by region (Asia versus non-Asia) to compare the ORR between the two treatment arms. In case the assumptions of the Cochran-Mantel-Haenszel test are violated due to a small number of subjects in some strata, a Fisher's exact test will be used. This analysis will be based on the ITT Analysis Set.

8.5.3.3 Other Secondary Endpoints

8.5.3.3.1 European Quality of Life - 5 Dimensions - 5 Levels

Observed and change from baseline values for the EQ-5D-5L index score will be summarized descriptively at planned visits during the Maintenance Phase, the Discontinuation Visit, and End-of-Treatment Visit by treatment arm. This analysis will be based on the HRQoL Analysis Set. The EQ-5D-5L Visual Analog Scale scores will be presented by data listing only.

[figure not shown]

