4.2 Secondary Objectives

Secondary objectives are as follows:

- To demonstrate superiority of maintenance therapy with avelumab versus continuation of first-line chemotherapy with regard to PFS as per RECIST v1.1 according to Investigator assessment.
- To demonstrate superiority of maintenance therapy with avelumab versus continuation of first-line chemotherapy with regard to the ORR as per RECIST v1.1 and per Investigator assessment
- To compare the subject-reported outcomes / quality of life (QoL) of subjects when treated with avelumab versus continuation of first-line chemotherapy as assessed by the European QoL 5-dimensions 5 Level Questionnaire (EQ-5D-5L), and the European Organization for Research and Treatment of Cancer (EORTC) QLQ-C30 and module QLQ-STO22
- To determine the safety and tolerability of avelumab.

5 Investigational Plan

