### 15.2.3 Subject-reported Outcomes/Health-Related Quality of Life

*Analysis sets: HRQoL*

- Health-related quality of life (HRQoL) will be assessed by the EuroQOL 5-dimensions questionnaire (EQ-5D), the European Organization for Research and Treatment of Cancer (EORTC) QLQ-C30 supplemented by the gastric cancer module QLQ-STO22 questionnaire. Details on these questionnaires are provided in the following sections. The analyses specified in this section will be performed for HRQoL analysis set. CCI

The following analyses will be performed for each of these score/scale systems: HRQoL questionnaires compliance and full completion rate

HRQoL compliance rate across all instruments will be summarized by considering the EQ-5D-5L, the QLQ-C30, and the QLQ-STO22 for each scheduled visit using the following definition:

$$\%Compliance = 100 \times \frac{\text{number of subjects with at least one HRQoL questionnaire available}}{\text{number of subjects for whom a HRQoL questionnaire is expected}}$$

$$\%Full\ completion\ rate = 100 \times \frac{\text{number of subjects with all items in HRQoL questionnaire available}}{\text{number of subjects for whom HRQoL questionnaire is expected}}$$

The compliance and full completion rate for each questionnaire will be displayed using a line plot with time on the x-axis and completion rate on the y-axis. Separate lines will be presented for each treatment arm.

- HRQoL questionnaires descriptive statistics

Observed and change from Maintenance Phase baseline values will be summarized descriptively at planned visits during the treatment phase, the Discontinuation visit, End of Treatment visit, and 30-day Safety Follow-up visit by treatment arm. The percent of subjects at the worst possible score and at the best possible score (see sub-sections below, for details on best and worst scores) will be reported. In addition, the best (biggest improvement), worst (largest decline), and last observed post-Maintenance Phase baseline change from Maintenance Phase baseline values will be summarized.

Change from Maintenance Phase baseline will also be displayed using a line plot with time point (scheduled visit) on the x-axis, mean change score on the y-axis, 95% CI's around each mean score, and separate lines for each treatment arm.

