If there are multiple complete assessments for any scheduled visit during the treatment phase, the assessment that is closest to the planned visit per protocol will be used in the analysis. If there are multiple complete assessments at Discontinuation visit and End of Treatment visit, the first assessment will be used in the analysis.

- Longitudinal analysis of change from Maintenance Phase baseline

A mixed-effects model repeated measures (MMRM) analysis will evaluate longitudinal change from baseline on the QLQ-C30 physical function scale and the QLQ-STO22 symptom scales. Covariates will include the Maintenance Phase baseline score for the domain score being evaluated and the randomization stratification factor. The questionnaire completion time point (Maintenance Phase-study day), including both scheduled and unscheduled visits, will be analyzed as a continuous variable. The overall significance of the difference between the MMRM trajectories for the treatment arms will be tested. An unstructured covariance structure will be used, if possible, though a simpler covariance structure will be used if the model does not converge.

- Subject level change from Maintenance Phase baseline

For the HRQoL domain scores analyzed using MMRM, an empirical cumulative distribution function (eCDF) curves, separated by treatment arm, will display the proportion of subjects who experienced specific changes from Maintenance Phase baseline to end of treatment. For each eCDF, the range of change scores will be displayed on the x-axis, and the cumulative percentage of patients achieving that change score or better will be displayed on the y-axis. The eCDF may be interpreted by choosing a change score magnitude that may be considered clinically meaningful on the x-axis and comparing the rate of subjects who achieved at least that amount of change (on the y-axis) between the treatment arms.

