### 15.2.3.1 European Quality of Life (EuroQoL) - 5 Dimensions - 5 Levels (EQ-5D-5L)

The EQ-5D questionnaire is a generic measure of health status that provides a descriptive profile and a simple index value. It includes 5 items assessing mobility, self-care, usual activities, pain / discomfort, anxiety / depression on a 5-level response scale (EQ-5D-5L). It also includes a visual analogue scale ranging from 0 to 100 for self-rated health status. A higher score indicates better health status. Utilities can be derived from the EQ-5D, ranging from 0.0 (worst health state) to 1.0 (best health state).

The EQ-5D-5L scoring system will also be converted into a single index value. The index value is country specific and is a major feature of the EQ-5D instrument, facilitating the calculation of quality-adjusted life years (QALYs) that are used to inform economic evaluations of health care interventions. The Japan country-specific value set will be used in deriving the index value for Asian countries and ranges from -0.111 (worst health state) to 1.000 (best health state); the UK country-specific value set will be used in deriving the index value for non-Asian countries – it ranges from -0.594 (worst health state) to 1.000 (best health state).

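### A secondary objective is to compare the arms on EQ-5D-5L, but the visible plan gives no between-arm estimate for it, and protocol and SAP disagree on whether the VAS is tabulated

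*Protocol*

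**What the plan says.** Protocol 4.2 sets the objective: "To compare the subject-reported outcomes / quality of life (QoL) of subjects when treated with avelumab versus continuation of first-line chemotherapy", with EQ-5D-5L named first of three instruments. The Protocol synopsis and SAP 5 repeat it.

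For the EQ-5D-5L index, Protocol 8.5.3.3.1 says: "Observed and change from baseline values for the EQ-5D-5L index score will be summarized descriptively at planned visits during the Maintenance Phase". For the VAS it says: "The EQ-5D-5L Visual Analog Scale scores will be presented by data listing only". Protocol 8.5.3.3.2 and 8.5.3.3.3 give the QLQ-C30 and QLQ-STO22 scales a between-arm MMRM with region and baseline as covariates.

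SAP 15.2.3 opens its list of HRQoL analyses with "The following analyses will be performed for each of these score/scale systems". The list includes observed and change values by visit and arm. On modelling it says: "A mixed-effects model repeated measures (MMRM) analysis will evaluate longitudinal change from baseline on the QLQ-C30 physical function scale and the QLQ-STO22 symptom scales". SAP 15.2.3.1 describes the VAS as part of the instrument and says of the index: "The Japan country-specific value set will be used in deriving the index value for Asian countries", with the UK set for all other countries.

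**The concern.** Two of the three instruments in one objective have a planned comparison and the third has none. Two results follow.

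- EQ-5D-5L is collected in both arms, but no difference with an interval is pre-specified. SAP 4 requires analyses not identified in it to be labelled as unplanned in the study report. An EQ-5D comparison added later would carry that label, in an open-label trial with a patient-reported outcome.
- The two documents give a programmer different instructions for the VAS: the protocol asks for a listing, while the SAP's general lead-in implies tables and plots by arm.

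The component certain to be tabulated, the index, is also the one built from two regional scales. The VAS runs from 0 to 100 and needs no value set.

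**Working it through.** The documents state no power, SD or target difference for EQ-5D-5L, so there is no planned figure to reproduce. The check is a trace through the text, then arithmetic on the value sets.

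**1. What each measure receives**

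| Measure | Protocol 8.5.3.3 | SAP 15.2.3 |
|---|---|---|
| QLQ-C30 | Summaries; MMRM on global health and five functional scales | Summaries; MMRM on physical function only |
| QLQ-STO22 | Summaries; MMRM on five symptom scales | Summaries; MMRM on symptom scales |
| EQ-5D-5L index | Summaries | Summaries; not in MMRM |
| EQ-5D-5L VAS | Listing | Summaries, if the general lead-in is taken literally; not in MMRM |

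**2. Could another output supply the contrast?** Three candidates in the SAP do not.

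- The line plots in 15.2.3 put a 95% CI around each arm's mean, not around the difference.
- The cumulative distribution curves are confined to scores that enter the MMRM.
- Section 8 claims accordance with protocol 7.0 apart from one item, the treatment start date for BSC-only subjects. It neither adds an EQ-5D model nor lifts the listing rule.

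**3. The two index scales (SAP 15.2.3.1)**

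- Japan set: 1.000 − (−0.111) = 1.111
- UK set: 1.000 − (−0.594) = 1.594
- Ratio: 1.594 / 1.111 = 1.43; difference: 1.594 − 1.111 = 0.483

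The same section also gives utilities a range of 0.0 to 1.0, which fits neither set.

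**4. Does pooling them distort the arm contrast?** For illustration, let every subject lose the same fraction p of the range that applies to their region, and let s be the Asian share of an arm's contributors at a visit.

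- Mean change in an arm = −p[1.111s + 1.594(1 − s)] = −p[1.594 − 0.483s]
- Avelumab minus control = 0.483 × p × (s for avelumab − s for control)

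This is zero when the shares are equal. Randomisation is stratified by Asia versus non-Asia (Protocol 8.2), so the shares should be close at the start. A spurious difference needs the regional mix of contributors to drift apart between arms, as it would if dropout differed by arm and region. The documents give neither p nor the shares, so no size can be put on it. What remains in any case is interpretation: an arm's mean index depends on its regional mix, and the same fractional loss counts for more outside Asia.

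**The case against.** **Compare need not mean model.** For PFS and ORR the objectives speak of demonstrating superiority; for quality of life they speak only of comparing. Summaries by arm, with a CI for each arm's mean in the plots, are a comparison of a kind. This stands in part, and it is why rewording the objective is an acceptable alternative. It is weakened because the same objective leads to a between-arm model for the other two instruments. Tables by visit are also an imperfect substitute: the first questionnaire after Day 1 falls at Week 3 for avelumab and 5-FU subjects but at Week 4 for capecitabine and BSC-only subjects (Protocol Tables 3 to 6).

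**The SAP may already summarise the VAS.** Protocol 8.5.1 lets the SAP modify the protocol's plans, and the lead-in in SAP 15.2.3 can be read that way. This stands. A reader might infer that the VAS will certainly go unsummarised; the documents support only an unresolved conflict. On either reading there is no between-arm estimate.

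**The gap may be closed elsewhere.** SAP 7 says a separate or supplemental plan might cover HRQoL, and text near the HRQoL section is redacted. A reader might infer that the trial cannot state an EQ-5D difference. That goes too far: the visible plan does not commit to one. The sentence limiting the MMRM is itself legible and explicit.

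**The value sets do no shown harm.** A reader might infer that the index contrast is biased. Stratification by region argues against that, and 1.43 compares theoretical ranges, not the part of each that subjects will occupy.

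**Conclusion.** The point holds as a gap in pre-specification and an inconsistency between documents. No visible text plans a difference, interval or test for either EQ-5D-5L component, although the objective is to compare the arms on that instrument. The protocol and SAP also need reconciling on the VAS.

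The two value sets are a matter of interpretability. Their ranges differ by a factor of 1.43, but bias in the contrast is conditional on the regional mix of contributors diverging between arms, which nothing in the documents shows.

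The importance is modest. Protocol 8.5.1 places EQ-5D-5L outside the testing hierarchy and applies no multiplicity adjustment to non-key secondary endpoints, so trial success and alpha are unaffected. The precision of an added estimate cannot be derived from the documents because no EQ-5D SD is given. The conclusion rests on the visible text and would lapse if an existing HRQoL plan already specified the contrast.

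**What to change.** 1. Replace the listing-only sentence in Protocol 8.5.3.3.1 so that observed and change values of the VAS are summarised by visit and arm, in line with SAP 15.2.3. If the protocol is not amended, record the change in SAP 8.
2. Add the index and the VAS to the MMRM in SAP 15.2.3, with Maintenance Phase baseline and region as covariates. Both covariates are already specified there.
3. State that the adjusted arm difference with 95% CI will be reported. The SAP currently states only a test of the difference between trajectories, even for the EORTC scales. Because completion day enters as a continuous variable, name the time points or interval to which the difference refers.
4. Repeat the index with one value set for all subjects, or by region, as a sensitivity analysis.

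The cost is some wording, two more outcomes in a model of the planned type, and an added output statement. No alpha is spent. The downside is a few more non-key secondary comparisons without multiplicity adjustment, on the same footing as the EORTC scales. If the sponsor does not want the model, the minimum is to settle the VAS rule and describe the objective as descriptive for EQ-5D-5L.
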